## **6.9 Covariates**

No adjustments for covariates are planned in the analyses.

## **6.10 Timing of Analyses**

The primary analysis of study will be conducted when all treated patients have had an opportunity to be followed for at least 6 months. Subsequent data cutoff dates may be defined to assess longer term clinical benefit with further follow up.

A safety analysis will be conducted at end of DLT period for each dose level in the safety run-in portion to evaluate the tolerability of dose-dense regimen.

# **7 PLANNED ANALYSES**

## **7.1 Disposition**

Patient disposition will be summarized by cohort and total for patients in FAS with descriptive statistics. Patients who discontinue study treatment and patients who withdraw from the study will be summarized along with reason for discontinuation or withdrawal. The

number of patients who signed the informed consent and the number and percentage of patients in each analysis set will be summarized. The reasons for screen failure will also be summarized, if applicable.

The number of patients enrolled at each site will be summarized.

## **7.2 Demographic and Baseline Characteristics**

Demographics and baseline characteristics, including age at consent, gender, ethnicity, race, baseline height, weight, and ECOG score will be listed and summarized by cohort and total using the FAS. Disease specific characteristics will be listed and summarized by cohort and total using the FAS. Disease characteristics may include cancer stage at diagnosis, previous cancer-related treatments, number of prior systemic therapies, number of prior cytotoxic chemotherapy in the PROC setting, platinum-free interval, histology, genetic markers, and tissue factor expression.

## **7.3 Protocol Deviations**

Important protocol deviations (defined as protocol violations by Seagen, Inc.) are those that represent a divergence from the protocol that could have a significant effect on the integrity of the study data, or on the patient's rights, safety, or welfare. Important protocol deviations also include exemptions to the study inclusion/exclusion criteria and will be summarized by category. A list of patients with important protocol deviations will be presented.

## **7.4 Treatment Administration**

Treatment administration will be summarized with descriptive statistics by cohort using the safety analysis set. Summaries may include but are not limited to the following:

- Duration of treatment (in weeks), for the Q3W cohort, which is defined as time from the first study dose to the earliest of Day 21 of the last treatment cycle, EOT visit, death date, or start date of subsequent anticancer therapy if applicable. For the dose-dense cohort, duration of treatment is defined as time from the first study dose to the earliest of Day 28 of the last treatment cycle, EOT visit, death date, or start date of subsequent anticancer therapy if applicable
- Number of cycles per patient
- Number and percentage of patients by number of treated cycles
- Cumulative dose received (in mg), which is defined as sum of the actual dose across all cycles.
- Average dose per week
- Relative dose intensity (RDI), which is defined as the absolute dose intensity (ADI) divided by the intended dose intensity (IDI). That is,  $RDI = ADI/IDI \times 100$ , where ADI is defined as the actual dose in mg/kg per week and IDI is defined as the intended dose in mg/kg per week regardless of dose reduction in later cycles. For

Q3W cohort IDI is  $2/3 = 0.667$  mg/kg/wk. For dose-dense cohort IDI is  $0.9*3/4=0.675$  mg/kg/wk if dose level is 0.9 mg/kg or  $0.65*3/4=0.488$  mg/kg/wk if 0.65 mg/kg.

- Number and percentage of patients whose dose was ever modified, which will be summarized by modification type (delay, reduction, elimination, unplanned dose adjustment). The number and percentage of doses that were modified may also be summarized.

## 7.5 Efficacy Analyses

All efficacy analyses will be descriptive in nature and all efficacy endpoints will be analyzed by cohort and total using the FAS unless otherwise specified. In addition, the ORR and DCR will also be analyzed using the EE set.

### 7.5.1 Primary Endpoint

#### 7.5.1.1 Confirmed Objective Response Rate (ORR)

The primary efficacy endpoint of this study is the confirmed ORR per investigator assessment. The confirmed ORR is defined as the proportion of patients who achieve a confirmed CR or PR according to RECIST v1.1 (Eisenhauer 2009). Patients who do not have at least 2 post-baseline response assessments (initial response and confirmation scan) will be counted as non-responders. Confirmation means a PR is followed by a PR or CR at least 4 weeks later, or a CR is followed by a second CR at least 4 weeks later.

The confirmed ORR of each cohort and its exact 2-sided 95% CI will be calculated.

This endpoint will also be summarized by the subgroups defined in Section 6.8.

### 7.5.2 Secondary Endpoints

#### 7.5.2.1 Confirmed and Unconfirmed ORR

Confirmed and unconfirmed ORR is defined as the proportion of patients who achieve a CR or PR according to RECIST v1.1 as assessed by the investigator. These include patients with confirmed responses as well as those whose responses were not confirmed or had not yet been assessed for confirmation. Patients who do not have at least 1 post-baseline response assessment will be counted as non-responders.

The confirmed and unconfirmed ORR will be estimated for each cohort and its exact 2-sided 95% CIs will be calculated.

#### 7.5.2.2 CA-125 Response Rate

Baseline CA-125 is the most recent non-missing measurement no more than 14 days prior to the first dose of study drug.

CA-125 response rate is defined as the proportion of patients who have at least a 50% reduction in CA-125 value from baseline. The response must be confirmed in a subsequent sample collected  $\geq 28$  days after the prior sample. The value of the confirmatory sample must

be  $\leq 110\%$  of the prior sample. The CA-125 evaluable analysis set will be used for the analysis of CA-125 response rate.

In addition, summary statistics of CA-125 values and changes from baseline will be tabulated by scheduled visit using the FAS.

### 7.5.2.3 Combined RECIST/CA-125 Overall Response

The combined RECIST/CA-125 overall response is defined as the proportion of patients whose best response is a CR or PR according to the Gynecological Cancer Intergroup (GCIG) combined RECIST and CA-125 criteria (Rustin 2011). For those who are not in the CA-125 evaluable analysis set, patients will be assessed to determine whether they have PD or not according to GCIG CA-125 criteria. Then the combined overall response will be assessed as indicated in Table 7.

**Table 1: Overall response by RECIST and CA-125 criteria**

RECIST Response	CA-125 Response	Combined RECIST/CA-125 Response
CR	Response and normalized a	CR
CR	Response	PR
CR	Not response and not PD b	PR
PR	Response	PR
PR	Not response and not PD b	PR
SD	Response	PR
SD	Not response and not PD b	SD
NE c	Response	PR
PD $>28$ days from CA-125 response	Response	PR
PD $\leq 28$ days from CA-125 response	Response	PD
PD	Not response and not PD b	PD
Any	PD b	PD

a Normalized means CA-125 value within the reference range

b Progression of CA-125 levels is defined as: 1) CA-125  $\geq 2 \times$  ULN on 2 occasions at least 1 week apart for patients with elevated CA-125 before treatment and later normalizes, 2) CA-125  $\geq 2 \times$  nadir value on 2 occasions at least 1 week apart for patients with elevated CA-125 before treatment which never normalizes, or 3) CA-125  $\geq 2 \times$  ULN on 2 occasions at least 1 week apart for patients with CA-125 in the reference range before treatment.

c Target lesions are not all evaluated, non-target lesions are non-PD, and no new lesions appear.

### 7.5.2.4 Disease Control Rate

DCR is defined as the proportion of patients who achieve a confirmed CR or PR according to RECIST v1.1 as assessed by the investigator, or meet the SD criteria at least once after start of study treatment at a minimum interval of 12 weeks (-1 week window). Patients who do not have at least 1 post-baseline response assessment or patients whose response cannot be assessed will be counted as not achieving disease control.

As an exploratory analysis, DCR will also be calculated without requiring confirmation of CR or PR for disease control.

DCR will be estimated for each cohort and its exact 2-sided 95% CIs will be calculated.

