- (Safety Run-In) Safety and tolerability of a dose-dense regimen of tisotumab vedotin, as measured by incidence of dose limiting toxicities (DLTs) or other unacceptable toxicities.
- (Parts A and B) Confirmed objective response rate (ORR) using Response Evaluation Criteria in Solid Tumors (RECIST) v1.1

Secondary Outcome Measures (Parts A and B)

- Safety and tolerability of tisotumab vedotin as measured by type, incidence, severity, seriousness, and relatedness of adverse events (AEs)
- Confirmed and unconfirmed ORR (all responses)
- Cancer Antigen 125 (CA-125) response rate according to Gynecologic Cancer Intergroup (GCIG) criteria
- Overall response according to GCIG combined RECIST and CA-125 criteria
- Duration of response (DOR)
- Disease control rate (DCR), proportion of patients with complete response (CR), partial response (PR), or stable disease (SD). SD patients will be included if maintained for a minimum of 12 weeks.
- Time to response (TTR)
- Progression-free survival (PFS)
- Overall survival (OS)
- Pharmacokinetic (PK) parameters and the incidence of antitherapeutic antibodies (ATA)

Additional (Parts A and B)

- Tissue Factor (TF) expression-response relationship
- Biomarkers of biological activity and resistance and predictive biomarkers of response
- In Part A and B US patients only, patient-reported outcomes as measured by an NCI PRO-CTCAE questionnaire customized to focus on visual symptoms, gastrointestinal symptoms, and bleeding, as well as Patient-Reported Outcomes Measurement Information System (PROMIS) version 2.0, short form 6b and other questions added by the sponsor.

Study Population

All patients must have PROC, defined as progression within 6 months from completion of platinum-containing therapy, and must be eligible for single agent chemotherapy. Safety run-in patients may have received more than 1 systemic treatment regimen for PROC. Patients eligible for Parts A and B patients must have received 1 to 3 prior anticancer lines of therapy overall, including at least 1 line of therapy containing bevacizumab or a biosimilar to bevacizumab.

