9.2.5 Disease Control Rate

Disease control rate (DCR) is defined as the proportion of patients who achieve a CR or PR according to RECIST v1.1 as assessed by the investigator, or meet the SD criteria at least once after start of study treatment at a minimum interval of 12 weeks (-1 week window). Patients who do not have at least 1 post-baseline response assessment will be counted as non-responders.

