### 6.4.2 Best Response

The determination of antitumor activity will be based on objective response assessments made by the investigator according to the RECIST v1.1 (Eisenhauer 2009). Only response assessments on or prior to the start date of any new anticancer therapy will be considered for best response. The patient’s best confirmed response will be the best demonstrated response to date that has been confirmed, when confirmation is required (i.e. for PR and CR only). When confirmation is not required, the patient’s best response will be the best demonstrated response to date. The patient’s best response will be used in determining the ORR.

A response (CR or PR) will be considered confirmed if the subsequent disease assessment conducted no earlier than 4 weeks after the initial response still shows CR or PR (i.e., CR followed by CR or PR followed by PR or CR). A patient will have a best response of SD if there is at least one SD assessment (or better)  $\geq 5$  weeks after the start of treatment and the patient does not qualify for confirmed CR or PR. RECIST v1.1 outlines scenarios for best overall responses when confirmation of CR and PR is required.

In addition to radiographic tumor assessments, expression level of CA-125 will also be monitored to assess CA-125 response according to the GCIG criteria.

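### The SAP's main disease control rate requires confirmed responses where the protocol does not, and read literally it can score an unconfirmed Week 12 PR below SD

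*SAP*

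**What the plan says.** Protocol 9.2.5 gives this definition of DCR: "the proportion of patients who achieve a CR or PR according to RECIST v1.1 as assessed by the investigator, or meet the SD criteria". The SD part applies from 12 weeks, with a one-week allowance. Nothing there asks for the response to be confirmed. The synopsis lists CR, PR or SD, again without confirmation, and adds "SD patients will be included if maintained for a minimum of 12 weeks".

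SAP 7.5.2.4 changes the response limb, so that a patient must "achieve a confirmed CR or PR according to RECIST v1.1 as assessed by the investigator, or meet the SD criteria at least once", and keeps the SD limb "at a minimum interval of 12 weeks (-1 week window"). It then says that, as an exploratory analysis, "DCR will also be calculated without requiring confirmation of CR or PR for disease control".

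SAP 6.4.2 has its own rule for a best response of SD: "A patient will have a best response of SD if there is at least one SD assessment (or better") at 5 weeks or later, provided that "the patient does not qualify for confirmed CR or PR". Section 7.5.2.4 neither refers to this rule nor repeats its 'or better'.

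SAP 9.1 lists no changes from the protocol, and SAP 9.2 says the document was updated to align with Amendment 4.

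**The concern.** There are two separate problems in one definition.

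First, the two documents define the same secondary endpoint differently, and nothing alerts the reader. The protocol writes 'confirmed' where it means it (9.2.1 for ORR, 9.2.6 for DOR, 9.2.7 for TTR), so its absence from 9.2.5 carries meaning. A report that follows the SAP would present as its main DCR a figure the protocol did not define, with the protocol's response limb shown at a lower tier.

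Second, the SAP's two limbs leave a gap. Protocol Appendix G defines SD as shrinkage short of PR and growth short of PD, so a PR scan does not itself meet the SD criteria. A patient who reaches PR at Week 12 and then progresses has no confirmed response and no SD scan at or after Week 11. On the literal wording that patient is not controlled, yet a patient with less shrinkage at the same scan is. Two programmers could reasonably classify this patient differently.

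**Working it through.** Neither document gives a target, precision or power figure for DCR, so there is no plan figure to reproduce. The check is a case comparison followed by a bound on size.

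**Step 1: classify four scan histories.** Scans fall at Weeks 6, 12 and 18, each ±7 days (protocol 6.5). The first scan therefore comes no later than Week 7, and the second no earlier than Week 11, which is inside the DCR allowance.

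| Scan history | Protocol 9.2.5 | SAP 7.5.2.4, literal | SAP 7.5.2.4 with 6.4.2's 'or better' | SAP exploratory DCR |
|---|---|---|---|---|
| A. SD Wk 6, PR Wk 12, PD Wk 18 | control | **no control** | control | control |
| B. SD Wk 6, SD Wk 12, PD Wk 18 | control | control | control | control |
| C. PR Wk 6, SD Wk 12 | control | control | control | control |
| D. PR Wk 6, PD Wk 12 | control | **no control** | **no control** | control |

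Row D shows that the documents disagree whichever way the SAP is read: the PR scan precedes Week 11, so the late limb cannot rescue it. Rows A and B show the inversion, which exists only on the literal reading.

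**Step 2: inputs for size.**
- 60 patients: the Part B target population (SAP 6.2).
- 12 responders, confirmed or not: an assumption (20% of 60). The 20% row in SAP 6.2 is for confirmed ORR, so it is not a plan value for all responses.
- Unconfirmed share 25% to 50%: SAP 8 expects about 75% of responses to be confirmed. In the ovarian data of protocol 1.3.3.2, 3 of 6 and 2 of 4 were confirmed.
- About 40% of responders first responding after the first scan: the complement of the 60% in SAP 8, which comes from GEN701. Applying it to unconfirmed responders assumes that confirmation does not depend on when the response appears.

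**Step 3: gap between the protocol and SAP definitions.** It cannot exceed the unconfirmed-response rate, because every confirmed responder counts under both.
- 12 × 0.25 = 3 patients; 3/60 = 5 points.
- 12 × 0.50 = 6 patients; 6/60 = 10 points.

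The all-response rates in protocol 1.3.3.2 widen the range: 6/36 × 0.25 = 4.2 points and 4/12 × 0.50 = 16.7 points. The actual gap is smaller, since unconfirmed responders with an SD scan at or after Week 11 (row C) already count.

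**Step 4: the inversion alone.** A Week 6 PR that persists at Week 12 is confirmed, one that falls to SD counts, and one that progresses is row D. So the exposed group is essentially those first responding after the first scan.
- 12 × 0.40 × 0.25 = 1.2 patients; 1.2/60 = 2 points.
- 12 × 0.40 × 0.50 = 2.4 patients; 2.4/60 = 4 points.

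Patients in this group who also have an SD scan at or after Week 11 come out, so the number is lower still. If unconfirmed responses cluster at later scans, the timing assumption fails and the ceiling moves back towards the 3 to 6 patients of Step 3.

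**The case against.** The strongest defence is SAP 6.4.2. Its SD rule is written for the patient without a confirmed response and accepts an assessment of SD or better. If 'SD criteria' in 7.5.2.4 is taken to mean that rule, applied at the 12-week threshold, row A becomes control and the inversion disappears. This stands as a possible reading, but not as the stated rule. Section 6.4.2 defines best response at 5 weeks, 7.5.2.4 sets a separate test at 12 weeks with no cross-reference, and the SAP does write 'or better' where it intends it (6.4.2, and again in 7.5.2.5).

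The sponsor may also say that the change is permitted and visible. Protocol 9.3 leaves the fuller plan to the SAP and requires a protocol amendment only when site conduct changes, and the SAP commits to reporting DCR without confirmation. Both points are fair: a stricter SAP definition is allowed, and readers will see both figures. What remains is that the protocol's response limb is demoted without being declared. The heading of SAP 9.1 refers to the original protocol, but 9.2 claims alignment with Amendment 4, whose section 9.2.5 has no confirmation requirement.

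Finally, little hangs on DCR. SAP 7.5 makes all efficacy analyses descriptive, the futility rule in SAP 8 counts responses, and the primary endpoint is confirmed ORR. That is right, and it limits the weight of the point.

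**Conclusion.** The difference between the documents is established: the SAP's main DCR requires confirmation, the protocol's does not, and a patient with PR at Week 6 and PD at Week 12 is classified differently on any reading. Under the stated assumptions (12 responders in 60, 25% to 50% unconfirmed) the gap is at most 5 to 10 points.

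The inversion is an ambiguity to close, not a settled feature of the plan. A reader might infer that the SAP definitely scores an unconfirmed Week 12 PR as no control. The text does not go that far, because 7.5.2.4 neither adopts nor excludes the 6.4.2 rule. Nor should the 5 to 10 points be read as the effect of the inversion. Given the further assumption on response timing, that effect is at most about 1 to 2 patients in 60 (2 to 4 points), and fewer once those with a later SD scan are removed.

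The primary endpoint and the interim futility decision are unaffected. The correction is worth making because the endpoint is otherwise not reproducible from its own definition.

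**What to change.** 1. In SAP 7.5.2.4, replace the SD limb with: at least one assessment of SD or better at 12 weeks or later (-1 week), without earlier PD. This settles row A.
2. State which definition is the main DCR, the confirmed one or the protocol's confirmation-free one, and report the other as the sensitivity analysis. Step 1 alone does not settle row D.
3. Either align SAP 7.5.2.4 with protocol 9.2.5, or keep the confirmed definition and record the departure, with its reason, in SAP 9.1.

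The cost is a few sentences in the SAP and a small change to the DCR derivation. No new data are needed. Under protocol 9.3 no protocol amendment is required, because site conduct does not change.

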#### **7.5.2.5 Duration of Response**

DOOR is defined as the time from the first documentation of objective response (CR or PR that is subsequently confirmed) to the first documentation of PD or death due to any cause, whichever comes first.

DOOR data will be censored as described below:

- Patients who do not have PD and are still on study at the time of an analysis will be censored at the date of last disease assessment documenting absence of PD.
- Patients who have started a new anticancer treatment prior to documentation of PD will be censored at the date of last disease assessment prior to the start of new treatment.
- Patients who are removed from the study prior to documentation of PD will be censored at the date of last disease assessment documenting absence of PD.
- Patients who have death or PD after two or more consecutive missed/NE tumor assessments will be censored at the date of the last adequate tumor assessment prior to the missed visits.

DOOR will only be calculated for patients who achieve a confirmed CR or PR according to RECIST v1.1 as assessed by the investigator.

DOOR will be analyzed by cohort using the Kaplan-Meier methodology and Kaplan-Meier plots will be provided. The median DOOR and its 2-sided 95% CI will be calculated as appropriate.

Sensitivity analyses may be performed for DOOR to evaluate the robustness of treatment effects:

- A sensitivity analysis may be performed by considering death or PD per RECIST v1.1 as an event regardless of missing disease assessments.
- A second sensitivity analysis may be performed for DOOR to evaluate the robustness of results by including investigator claim of clinical progression as an event. Patients who are not evaluable or have a response of SD or better per RECIST v1.1 at the same visit as investigator claim of clinical progression will be counted as disease progression (i.e., an event). The date of progression will be the date of investigator claim of clinical progression or PD date per RECIST v1.1, whichever is earlier.

#### **7.5.2.6 Time to Response**

TTR is defined as the time from the start of study treatment to the first documentation of objective response (CR or PR that is subsequently confirmed).

Patients who do not achieve objective response will have the TTR censored as described below:

- Patients with a PFS event (i.e., disease progression or death due to any cause) or who start a new anticancer treatment will be censored at the trial-maximum follow-up time (i.e., last patient last visit – first patient first visit + 1).
- All other patients will be censored at the date of last disease assessment.

TTR will be analyzed by cohort using the Kaplan-Meier methodology and Kaplan-Meier plots will be provided. The median TTR and its 2-sided 95% CI will be calculated as appropriate.

In addition, TTR will be summarized for patients who achieve a confirmed CR or PR.

#### **7.5.2.7 Progression-Free Survival (PFS)**

PFS is defined as the time from the start of study treatment to the first documentation of PD or death due to any cause, whichever comes first.

The same censoring rules as outlined in Section 7.5.2.5 for DOR will be applied to PFS. Patients who are known to have died and do not have an evaluation of tumor response after their first dose of study drug will be censored at Day 1.

PFS will be analyzed by cohort using the Kaplan-Meier methodology and Kaplan-Meier plots will be provided. The median PFS and its 2-sided 95% CI will be calculated as appropriate. The PFS rates at 3 and 6 months, and every 3 months thereafter, will be reported and their 2-sided 95% CIs will be calculated.

Sensitivity analysis of PFS will be performed as described in Section 7.5.2.5 for DOR.

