Interim futility analysis will be performed on Part B after at least 20 patients with 1 to 3 prior lines of therapy, including bevacizumab treatment, have been treated and had at least one response assessment post-baseline. The Bayesian predictive probability approach will be used to determine the futility criteria ([Lee 2008](#)). At the time of the interim futility analysis, the predictive probability of success (PPoS) will be calculated. Based on activity and safety data, together with the PPoS, the cohort may continue or be stopped early by the sponsor. While the interim futility analysis is performed, enrollment in Part B may continue. A cohort may also be discontinued at any point at the discretion of the sponsor.

On a periodic basis, a Safety Monitoring Committee (SMC) will monitor the safety of patients participating in the trial. The SMC will be responsible for evaluating the results of safety analyses and will make recommendations to the sponsor. Ongoing, real-time review of patient safety and serious adverse events (SAEs) will also be conducted by the sponsor's Drug Safety department throughout the study.

During the safety run-in period, the SMC will assess tolerability and safety of tisotumab vedotin (refer to SMC charter for additional details) at the end of the DLT period for each dose level. Ad hoc meetings of the SMC may be convened prior to the safety evaluation period if safety data indicate.

An individual's dose may be modified based upon treatment-related AEs. Response will be assessed every 6 weeks for the first 6 months, every 12 weeks for the next 6 months, and then every 6 months after that. RECIST v1.1 will be used by the investigator to score responses for primary and secondary endpoints as well as progression. Objective responses will be confirmed with repeat scans at least 4 weeks after the first documentation of response. The study will be closed 3 years after the last patient is enrolled or when no patients remain in long-term follow-up, whichever comes first. Additionally, the sponsor may terminate the study at any time.

Figure 2: Study design

Safety run-in will start with 3Q4W dosing of 0.9 tisotumab vedotin in approximately 12 patients. If deemed safe, this dose will escalate to 1.2 mg/kg. If not deemed safe, it will de-escalate to 0.65 mg/kg. Part B will enroll only after the 0.9 mg/kg 3Q4W dose is deemed safe by the SMC.

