9.2.6 Duration of Response

DOR is defined as the time from the first documentation of objective response (CR or PR that is subsequently confirmed) to the first documentation of PD or death due to any cause, whichever comes first.

DOR data will be censored as described below:

- Patients who do not have PD and are still on study at the time of an analysis will be censored at the date of last disease assessment documenting absence of PD.
- Patients who started a new anti-cancer treatment prior to documentation of PD will be censored at the date of last disease assessment prior to the start of new treatment.
- Patients who are removed from the study prior to documentation of PD will be censored at the date of last disease assessment documenting absence of PD.

- Patients who progressed or died after an extended loss to follow up (i.e., ≥ 2 consecutive missed disease assessments) will be censored at the date of the last disease assessment prior to the missed visits.

DOR will only be calculated for patients who achieve a confirmed CR or PR according to RECIST v1.1 as assessed by the investigator.

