9.2.8 Progression-Free Survival

PFS is defined as the time from the start of study treatment to the first documentation of PD or death due to any cause, whichever comes first.

The same censoring rules as outlined in Section 9.2.6 for DOR will be applied to PFS. Patients who are not known to have died and who do not have an evaluation of tumor response after their first dose of study drug will be censored at Day 1.

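### The SAP's PFS rule has lost the word *not*: it censors at Day 1 the patients known to have died without a scan, which biases PFS upward wherever such early deaths occur

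*SAP*

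**What the plan says.** SAP 7.5.2.7 measures PFS from the start of treatment to the "first documentation of PD or death due to any cause, whichever comes first". It adopts the DOR censoring rules of SAP 7.5.2.5 and adds a Day 1 rule of its own: those that "are known to have died and do not have an evaluation of tumor response after their first dose of study drug will be censored".

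The matching sentence in Protocol 9.2.8 begins "Patients who are not known to have died and who do not have an evaluation of tumor response" and also ends in censoring at Day 1. The two sentences are otherwise nearly identical.

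Three other provisions bear on the point:

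- **TTR.** SAP 7.5.2.6 opens a censoring rule with "Patients with a PFS event (i.e., disease progression or death due to any cause", so it too treats any death as a PFS event.
- **Missed scans.** SAP 7.5.2.5 states: "Patients who have death or PD after two or more consecutive missed/NE tumor assessments will be censored" at the last adequate assessment. Protocol 9.2.6 has the same rule for "Patients who progressed or died after an extended loss to follow up".
- **Sensitivity analysis.** SAP 7.5.2.5 offers: "A sensitivity analysis may be performed by considering death or PD per RECIST v1.1 as an event regardless of missing disease assessments". SAP 7.5.2.7 carries the DOR sensitivity analyses over to PFS.

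SAP 9.1 declares no change from the protocol. SAP 9.2 says the SAP was updated to align with Amendment 4, whose PFS section contains *not*.

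**The concern.** A Day 1 rule is a fallback for patients about whom nothing is known after the first dose. SAP 7.5.2.8 uses it that way for OS. A known death is information, and for PFS it is the event itself. Applied to known deaths, the rule removes some of the worst outcomes from the analysis, and the error always favours the drug once those deaths have occurred.

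The 3-month, 6-month and later PFS rates and the median are exposed. PFS is also looked at during the Part B interim (SAP 8), though without a threshold. Part A expansion depends partly on other efficacy endpoints being comparable with standard of care (SAP 6.2); PFS is not named there.

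The reversal also leaves living patients with no post-dose scan without an explicit rule. The inherited DOR rules send them to their last assessment without PD, which can only be a pre-treatment scan. This should not move the curve, but it leaves their censoring date undefined.

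**Working it through.** The plan states no PFS assumption (median, rate or event count), so there is no figure of its own to reproduce.

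**1. The two rules side by side**

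| No tumour evaluation after first dose | Protocol 9.2.8 | SAP 7.5.2.7 as written |
|---|---|---|
| Not known to have died | Censored at Day 1 | No explicit rule |
| Known to have died | Event at date of death | Censored at Day 1 |

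**2. Which deaths are affected.** Protocol 3.1: "Response will be assessed every 6 weeks for the first 6 months". Protocol 6.5 allows ±7 days, so the second scan falls due at week 12 and no later than week 13. An unscanned patient who dies after missing both scans is censored under either document. So is one who started new anticancer therapy first. The missing word therefore changes the handling only of unscanned deaths before about weeks 12–13 without new therapy.

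**3. Effect on the curve.** Let N be the cohort size, k the number of such deaths and e the number of events among the other patients by time t. Take t later than the last of the k deaths, with no other censoring before t.

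- Protocol rule: S(t) = (N − k − e)/N
- SAP rule: S(t) = (N − k − e)/(N − k)
- Ratio, SAP to protocol: N/(N − k)

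Before the deaths occur the SAP curve is marginally lower, because its risk set is smaller.

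**4. Numbers.** The documents do not give k. The cohort sizes are those in SAP 6.2. The true 6-month PFS of 25.0% is an assumption.

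| N | k | 25.0% × N/(N−k) |
|---|---|---|
| 30 | 1 | 25.9% |
| 30 | 3 | 27.8% |
| 60 | 1 | 25.4% |
| 60 | 3 | 26.3% |
| 60 | 6 | 27.8% |
| 100 | 1 | 25.3% |
| 100 | 5 | 26.3% |

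In terms of the share d = k/N, the reported rate is 25.0%/(1 − d). If PFS is exponential with a true median of 3.0 months (also assumed), the reported median is 3.0 × ln(2/(1 − d))/ln 2. The chance that a cohort has no such death, and so no bias, is (1 − d)^N.

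| d | 6-month PFS | Median (months) | No such death, N=30 | No such death, N=60 |
|---|---|---|---|---|
| 1% | 25.3% | 3.04 | 74% | 55% |
| 3% | 25.8% | 3.13 | 40% | 16% |
| 5% | 26.3% | 3.22 | – | – |
| 10% | 27.8% | 3.46 | 4% | 0.2% |

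**5. Check by direct Kaplan-Meier calculation.** With N=60, k=3 and an assumed median of 4 months in the other patients, protocol versus SAP gives:

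- 3-month PFS 56.7% versus 59.6%
- 6-month PFS 33.3% versus 35.1%
- median 3.61 versus 4.00 months

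Adding uniform censoring between 3 and 18 months, in 3,000 simulated cohorts the SAP rule gave higher 3- and 6-month PFS every time (mean +3.0 and +1.8 percentage points). The median was never lower (mean +0.38 months). A second simulation used 6-weekly scans ±1 week and unscanned deaths spread over weeks 1–12. Its 6-month ratios were 1.030–1.032, 1.051–1.053 and 1.111–1.112 for d = 3%, 5% and 10%; 1/(1 − d) is 1.031, 1.053 and 1.111.

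**6. Scale.** Ignoring censoring, the 95% half-width around 25% is 1.96 × √(0.25 × 0.75/N): about 11 points at N=60 and about 15 at N=30.

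**7. Possible knock-on to TTR.** Under SAP 7.5.2.6, patients with a PFS event stay in the TTR risk set to the trial-maximum follow-up. If that rule were programmed from the PFS event flag, the affected deaths would instead be censored at the last disease assessment, and the TTR curve would rise by the same factor. An assumed 20.0% responding becomes 20.7% (N=30, k=1), 22.2% (N=30, k=3) or 21.1% (N=60, k=3).

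**The case against.** The textual contradiction cannot be defended; the case on the other side concerns size and weight.

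- **The effect is probably small.** The nearest figure in the documents is in Protocol 1.3.3.1: 6 of 207 patients (2.9%) died within 30 days of last dose in the two earlier trials, whatever their scan status. Entry here requires ECOG 0–1 and a life expectancy of at least 3 months (Protocol 4.1). At 2.9%, 25.0% becomes 25.7%, well inside the confidence interval. This stands as a guide to scale, though it is a different quantity in mixed tumours. The d = 10% row is an upper illustration without support in the documents. A confidence interval does not, however, allow for a systematic error.
- **The smooth medians mislead.** Progression is dated to scans, so the Kaplan-Meier median moves in jumps. In a simulation with 6-weekly scans and an assumed underlying median of 3.0 months (N=60, k=3), the shift was under 0.1 month in about 53% of runs and over 1 month in about 18%. This stands: the exponential medians show direction and rough size only.
- **TTR as written is unaffected**, because SAP 7.5.2.6 spells out its own PFS event. This stands; the knock-on arises only if the PFS flag is reused in programming.
- **A sensitivity analysis would show the difference.** Only in part. SAP 7.5.2.7 says PFS sensitivity analysis will be done, but the relevant one is optional in SAP 7.5.2.5. It addresses missing assessments rather than the Day 1 rule, and it leaves the main estimate uncorrected.
- **PFS is secondary and descriptive.** True, and it limits the stakes. It does not make a rule that contradicts the endpoint's definition acceptable.

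**Conclusion.** The SAP sentence is wrong as written. It contradicts Protocol 9.2.8, the PFS definition in its own section and SAP 7.5.2.6, and no change from the protocol is declared. Programmed literally, it raises PFS by a factor of about N/(N−k) once the affected deaths have occurred. For shares of 1% to 5%, an assumed 25.0% six-month rate is reported as 25.3% to 26.3%. These sizes rest on assumed values of k, d and underlying PFS, and on no other early censoring. A cohort with no unscanned death before about weeks 12–13 shows no bias. Confirmed ORR, the PPoS criterion and OS are untouched. The point must be fixed because the error is unambiguous, can be programmed as it stands and favours the drug, not because a large effect is expected.

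**What to change.** In SAP 7.5.2.7, restore *not*, so that Day 1 censoring applies to patients who are not known to have died and have no tumour evaluation after the first dose. A death without a post-dose scan then counts as a PFS event on the date of death, subject to the rules in SAP 7.5.2.5 on two or more missed or non-evaluable assessments and on new anticancer therapy. The same word restores the explicit rule for living patients without a scan.

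Check the program line that derives PFS censoring and correct it if it follows the present SAP text. If the TTR derivation uses the PFS event flag, confirm that these deaths are handled as SAP 7.5.2.6 states.

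The cost is one word in one SAP sentence and the matching program line. Data collection, sample size and study conduct do not change.
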